2.2 Study Objectives

Objective 1: Define the study population

To describe pre-biologic demographic, clinical and functional characteristics of patients initiating biologics, overall and by biologic class.

Objective 2: Quantify levels of response and characterize patients by levels of response

- To operationally assess levels of response to biologics (from non-response to highest level of response) in individual domains and using different composite definitions based on exacerbation rates, long-term oral corticosteroid doses, asthma symptoms control, and lung function;
- To characterize patients by levels of composite definitions of response and compare patient characteristics between levels, overall and by biologic class.

Objective 3: Quantify components of clinical remission and characterize patients according to different definitions

- To operationally assess remission after biologic initiation in individual domains and using different composite definitions based on exacerbation rates, long-term oral corticosteroid use, asthma symptoms control, and lung function;
- To characterize patients by categories of composite definitions of remission and compare patient characteristics between categories, overall and by biologic class.

3.0 Study Design

This study is a registry-based cohort study. The study consists of pre-biologic (baseline) and post-biologic (follow-up) periods (Figure 1). Variables describing the patient baseline demographic and clinical characteristics are obtained during pre-biologic visits, which are prior to or on biologic treatment initiation date. Patient baseline characteristics are available at biologic initiation (eg, age and long-term OCS use), in the year preceding biologic initiation (eg, count of exacerbation episodes), or at any time points pre-biologic initiation (eg, highest blood eosinophil concentration and allergy test results).

Post-biologic period is from biologic initiation date until a follow-up visit closest to a 1-year period with a minimum of 24 weeks of follow-up time (48 weeks for exacerbation rates). ISAR data structure consists of data collected at the time of regular follow-up visits to the doctor, including numbers of exacerbations and change in medication intake (eg, long-term OCS) since the previous visit. In patients who have at least 1 follow-up visit, 80% have post-biologic data available at the 1-year mark +/- 1 month. We aim to use 1-year of follow-up if more than one follow-up visit data is available, thus if a patient had follow-up visits equidistant from before and after 1-year the biologic initiation date, we will use the second follow-up of >1-year in this occasion (maximum 18 months since biologic initiation).

During this post-biologic period, we will assess four asthma clinical and functional endpoints (domains) chosen based on a review of biologic effectiveness studies (Table 1), responder publications (Table 2), and three Delphi based studies (Table 3). The composite definitions will at the minimum consider exacerbations and long-term OCS use. Asthma symptoms control and/or lung function will also be considered.

It should be noted that, while remission can also be defined as a period of time with low to no disease activity (durable remission, on- or off-treatment), this goes beyond the scope of the present project where the disease activity will be assessed at approximately 1-year time after initiating biologics.

[figure not shown]

Figure 1. Study design. Note: Patients enrolled in ISAR who initiated anti-TSLP have not yet been followed up.

4.0 Study Population

4.1 Data Sources

Data will be sourced from the International Severe Asthma Registry (ISAR) (51). ISAR is a multi-country, multicentre, observational initiative with retrospective and prospective data collection. Data collection started in 2017 and is currently ongoing. ISAR includes patients ≥18 years old who receive treatment according to GINA Step 5 or experience uncontrolled asthma at GINA Step 4 as per the definition of severe asthma (5, 27). As of July 2022, ISAR had 13,164 patients registered in the database, out of whom 5,961 had a history of biologic treatment. Its strength comes from the collection of patient level, pseudonymous, real-life, standardized (using a core set of agreed variables) data from 24 countries and over 248 sites across the world. Data are collected via electronic Clinical Record Forms (eCRF) made available by a common web-based platform in 14 countries. Another 9 countries collect data using their own eCRF systems, and for the USA data are extracted from electronic medical records (EMR). Data are then processed in a standardized manner to produce overall ISAR datasets.

4.2 Inclusion and Exclusion Criteria

Inclusion Criteria

- Patients who are receiving treatment according to GINA (2020 Criteria) step 5 or are uncontrolled at step 4. Uncontrolled asthma is defined as having severe asthma symptoms or frequent exacerbations (≥2/year) requiring oral corticosteroids;
- Patients prescribed with a biologic (anti-IL5/5R, anti-IgE, anti-IL4/IL13, or anti-TSLP) for the first time;
- Patients 18 years or older at biologic initiation;
- Available registry data prior to or on biologic therapy initiation date for at least one of the studied domains: exacerbation rate (number of episodes in the year preceding biologic initiation), long-term OCS use (at biologic initiation), asthma symptoms control (as assessed closest to biologic initiation in the year preceding to initiation), lung function (as assessed closest to biologic initiation in the year preceding to initiation);
- Available registry data for at least one paired domain at follow-up visit that is closest to a 1-year period (min. 24 weeks for long-term OCS use, asthma symptoms control, and lung function; min. 52 weeks for exacerbations).
 - Note: follow-up data for patients enrolled in ISAR who initiated anti-TSLP is not yet available and as such, they are currently not eligible. However, subject to funding and

sufficient numbers, the analysis could be revisited in a year time when this data becomes available.

Exclusion Criteria

- Patients who received bronchial thermoplasty prior to initiating biologics.

5.0 Study Variables and Study Outcome Definitions

While clinical remission will be assessed in all patients irrespective of their status prebiologic initiation, response can only be assessed in patients impaired when initiating the treatment. Impairment will be defined for each domain independently as: 1) exacerbations: ≥2 exacerbations in the year preceding biologic initiation; 2) long-term OCS use: patients receiving long-term (daily) OCS at biologic initiation; 3) asthma symptoms control: partly or uncontrolled patients at biologic initiation, based on GINA 2020 asthma symptoms control categories (5); 4) lung function: patients <80% FEV1 predicted pre-biologic initiation.

5.1 Individual response/remission domains

5.1.1 Exacerbation rates

Exacerbations during the follow-up will be counted from the day of the biologic initiation to the day closest to the 1-year mark post-initiation. A minimum of 48 weeks of follow-up will be required.

Response definition (in patients with ≥2 exacerbations in the year preceding biologic initiation)

Non-response: <50% reduction from pre- to post-biologic initiation
 Response: ≥50% reduction from pre- to post-biologic initiation

Post-biologic categories considered for remission definitions (in all patients, irrespective of pre-biologic status)

- ≥1 that required hospitalisation, or ≥3 of any severity
- 2 that did not require hospitalisation
- 1 that did not require hospitalisation
- None

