5.3 Analytical variables

Table 4. List of variables that will be used for the analysis.

Label	Type	Value	Construct/comments
Meta data ¹			
Calendar year at biologic	Numerical	-	
initiation			
Follow-up duration	Numerical	-	At least 24 weeks and as close as
(weeks)			possible to 1 year
Biologic therapy variables ¹			
Type of biologics	Nominal	Anti-IgE, anti-IL5/5R, anti-IL4/13, anti-TSLP	
Biologic therapy	Binary	0=Switched/stopped	Data indicating a discontinuation of initial
maintenance	,	1=Continue	biologic in the first year of follow-up
Asthma-related outcome v	ariables ²		
Exacerbation rates			
Exacerbation rate at	Discrete	-	Number of exacerbations in the year
biologic initiation			preceding biologic initiation.
Rate of exacerbations	Discrete	-	Number of exacerbations requiring
requiring hospitalisation			hospitalisation in the year preceding
at biologic initiation			biologic initiation.
Exacerbation rate at	Discrete	-	Number of exacerbations during the year
follow-up			following biologic initiation.
Rate of exacerbations	Discrete	-	Number of exacerbations requiring
requiring hospitalisation			hospitalisation during the year following
at follow-up			biologic initiation.
Reduction of ≥50% in	Categorical	Yes	N/A for patients <2 exacerbations in the
exacerbation rate	3	No	year preceding biologic initiation.
between baseline and		N/A	, , , , , ,
follow-up			
Long-term OCS use ²	'		
Long-term OCS dose at	Numerical	-	Prednisone-equivalent dosages.
biologic initiation (mg/day)			
Long-term OCS dose at	Numerical	_	Prednisone-equivalent dosages.
follow-up (mg/day)	Numerical		Treumsone-equivalent dosages.
Reduction of ≥50% in	Categorical	Yes	N/A for patients not receiving long-term
long-term OCS dose	Categorical	No	OCS at biologic initiation
between baseline and		N/A	OGG at biologic illitiation
follow-up		19/7	
Asthma symptoms control ²	2		 
Asthma symptoms Asthma symptoms	Ordinal	Well controlled	GINA 2020 classification (used by most
control assessment at	Jidillal	Partly controlled	participating centres). For centres
biologic initiation		Uncontrolled	reporting asthma symptoms control
biologic iriliation		Oricontrolled	
			assessment based on ACT (52) and/or
			ACQ (53), algorithms will be used to fit
			available data to GINA 2020 categories: - ACQ:
			0.75< Mean ACQ <1.5: Partly controlled Mean ACQ ≥1.5: Uncontrolled
			- ACT: Total ACT >19: Well controlled
			15< Total ACT ≤19: Partly controlled
			Total ACT ≤15: Uncontrolled

		1	

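### The follow-up exacerbation window is defined inconsistently and, as written, unscaled counts over unequal periods are compared with a fixed one-year baseline

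*Protocol*

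**What the plan says.** **Baseline.** Section 4.2 takes the "number of episodes in the year preceding biologic initiation", so the reference period is a fixed year.

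**End of follow-up.** Section 3.0 runs the post-biologic period "until a follow-up visit closest to a 1-year period", with a minimum of "48 weeks for exacerbation rates". For visits equally far from one year on either side, "we will use the second follow-up of >1-year in this occasion (maximum 18 months since biologic initiation"). Section 5.1.1 states: "Exacerbations during the follow-up will be counted from the day of the biologic initiation to the day closest to the 1-year mark post-initiation". It adds: "A minimum of 48 weeks of follow-up will be required". Section 4.2 sets the minimum for exacerbations at 52 weeks.

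**How counts are recorded.** Section 3.0 says data are collected at regular visits, "including numbers of exacerbations and change in medication intake (eg, long-term OCS) since the previous visit".

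**Outcome.** Table 4 labels the follow-up variable a rate but types it as discrete and defines it as "Number of exacerbations during the year" after initiation. Section 5.2.1 (Remission) likewise refers to the year after initiation. Response is a reduction of at least 50% in patients with two or more baseline events. Remission allows no event (strict) or at most one, not hospitalised (relaxed).

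**Timing of visits.** Section 3.0 reports that, of patients with at least one follow-up visit, 80% have data within one month of the one-year mark.

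**The concern.** The outcome is called a one-year count in some places, while in section 3.0 its length is set by a visit date. If a patient's chosen visit falls after one year and the recorded count is used as it stands, that patient has had more time to accumulate events than the baseline year allowed. The three thresholds (50% reduction, none, at most one) are then applied to a count whose exposure differs between patients.

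The error leans one way. Under the 48-week minimum the window can be 4 weeks short of a year but about 26 weeks long, and ties go to the later visit. For example, a patient with 4 baseline events and 3 events over 18 months has 2 per year, a 50% reduction; on raw counts the reduction is 25% and the patient is a non-responder.

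Section 3.0 puts exacerbations in every main composite, so the composites inherit the problem. The study also compares response and remission across countries, biologic classes and patient characteristics, and any difference in visit timing between such groups would be mixed into those comparisons. This concerns the definition of the outcome, so it is not a detail that can simply be left to the analysis plan.

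**Working it through.** The protocol has no figure of its own to reproduce here; Table 5 lists registry counts only.

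**Inputs from the protocol.** Baseline window 1 year; shortest follow-up 48 weeks (sections 3.0 and 5.1.1) or 52 weeks (section 4.2); longest 18 months, taken as 78 weeks; 80% of patients within ± 1 month.

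**Assumption.** The post-biologic event rate is not given. I use a constant 1 event per year, with 0.5 to 2 per year as a range.

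**Step 1: exposure.** Mean count m = rate × weeks / 52. At 1 per year, m = 0.92 at 48 weeks, 1.00 at 52 and 1.50 at 78.

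**Step 2: probability of meeting each rule.** Poisson: P(0) = exp(−m) and P(≤1) = exp(−m)(1 + m). Negative binomial with dispersion 1: P(0) = 1/(1 + m) and P(≤1) = 1/(1 + m) + m/(1 + m)². P(≤1) is also the probability of response for a baseline of 2 or 3 events.

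| | 48 weeks | 52 weeks | 78 weeks |
|---|---|---|---|
| Poisson P(0) | 0.40 | 0.37 | 0.22 |
| Poisson P(≤1) | 0.76 | 0.74 | 0.56 |
| Neg. binomial P(0) | 0.52 | 0.50 | 0.40 |
| Neg. binomial P(≤1) | 0.77 | 0.75 | 0.64 |

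From 52 to 78 weeks the drop is 10 to 18 points with no change in the underlying rate. Within 11 to 13 months the Poisson values move only from 0.40 to 0.34 for P(0) and from 0.77 to 0.71 for P(≤1).

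**Step 3: pooled effect.** Suppose the entire remaining 20% are seen at 78 weeks. Poisson: 0.20 × (0.368 − 0.223) = 2.9 points for P(0), and 0.20 × (0.736 − 0.558) = 3.6 points for P(≤1). Negative binomial: 0.20 × 0.10 = 2.0 and 0.20 × 0.11 = 2.2 points. Over Poisson rates of 0.5 to 2 per year the same calculation gives 1.7 points (P(0) at 2 per year: 0.20 × (0.135 − 0.050)) to 4.3 points (P(≤1) at 1.5 per year: 0.20 × (0.558 − 0.343)).

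**Step 4: does annualising repair the 50% rule?** Annualised count = count × 52 / weeks.
- Baseline 2, visit at 78 weeks: the annualised count must be at most 1. Two events give 2 × 52/78 = 1.33, so only 0 or 1 qualifies, as before. P(response) stays 0.56 against 0.74 at one year.
- Baseline 3, visit at 78 weeks: the limit is 1.5, so two events now qualify. P(≤2) with m = 1.5 is 0.81, which overshoots 0.74.
- Baseline 2, visit at 48 weeks: one event gives 52/48 = 1.08, so a fall from 2 to 1 becomes non-response.

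Integer counts defeat the scaling, and it cannot help a zero-event rule at all.

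**The case against.** The strongest reply is that the protocol never adopts an 18-month count. The 18-month limit appears once, in the sentence on equidistant visits; section 5.1.1 points to the one-year mark, and section 5.2.1 and Table 4 speak of the year after initiation. That stands: the accurate charge is unreconciled wording with no stated handling of later counts, and 18 months is an outer limit, not a typical window.

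A reader might also infer the following, none of which the documents support:
- **Later counts cannot be cut at one year.** The protocol says only that numbers are collected since the previous visit. It does not say that event dates are unavailable, and intermediate visits may sometimes allow truncation.
- **Visit spacing differs by country or site.** No timing by country or class is given. The 10 to 18 point shift applies only to a group seen at 18 months, and no such group is shown.
- **Follow-up duration is ignored.** Table 4 lists it among the variables for analysis, and how it enters a model may be set out in an analysis plan not seen here.

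Finally, the pooled effect is small, and 2 to 4 points is a loose upper bound. The 80% refers to everyone with a follow-up visit, so the other 20% includes patients seen too early to enter the exacerbation domain. All of this limits the size of the problem; none of it settles which window the analyst should use.

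**Conclusion.** The point holds as an inconsistency in the outcome definition with a modest, directional consequence. Sections 3.0, 4.2, 5.1.1, 5.2.1 (Remission) and Table 4 do not agree on one exacerbation window, and two analysts could classify the same patient differently. Read with section 3.0, raw counts over unequal periods are set against a one-year baseline, and late-seen patients are pushed toward non-response and non-remission.

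At an assumed 1 event per year, a patient seen at 78 weeks rather than 52 is 10 to 18 points less likely to meet a rule, depending on the rule and on Poisson or negative binomial counts. The pooled proportions move by at most about 2 to 4 points. Distortion of comparisons between countries, biologic classes or subgroups is a risk to check, not a demonstrated bias. The figures rest on the assumed rate, a constant hazard and the protocol's own 80%.

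**What to change.** 1. Reconcile sections 3.0, 4.2, 5.1.1, 5.2.1 (Remission) and Table 4 on one exacerbation window, including 48 versus 52 weeks as the minimum.
2. Base the main exacerbation response (at least 50% reduction) and remission (none; at most one) results, and the composites that use them, on unscaled counts covering 12 ± 1 months, subject to the reconciled minimum. Where event dates or intermediate visits allow, cut later counts at one year so that those patients stay in the main analysis.
3. Report all visits up to 18 months as a sensitivity analysis. Do not rely on annualised counts for the 50% rule: they leave a baseline of 2 uncorrected and over-correct a baseline of 3.
4. Tabulate follow-up weeks by country and biologic class, and show the association models with and without follow-up weeks as a sensitivity analysis. Forcing it into the main models is not advised, since visit timing arises after initiation and may reflect disease course.

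**Cost.** Wording changes, a derived window variable and a sensitivity analysis. Up to about 20% of patients move from the main exacerbation-based results to the sensitivity analysis, with some loss of precision. That matters most for the smallest composite, which has 134 patients in Table 5.

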5.1.2 Long-term OCS use

Response definition (in patients receiving long-term OCS at biologic initiation)

Non-response: <50% reduction in daily dose from pre- to post-biologic initiation

• Response: ≥50% reduction in daily dose from pre- to post-biologic initiation

Post-biologic categories considered for remission definitions (in all patients, irrespective of pre-biologic status)

- >10mg/day
- >5 to 10mg/day
- >0 to 5mg/day
- No long-term OCS use

5.1.3 Asthma symptoms control

Well/partly/uncontrolled categories as defined by GINA 2020 (5) will be used. Whenever ACQ or ACT scores were provided in lieu of GINA categories, conversions will be applied as detailed in section 5.3.

Response definition (in patients uncontrolled or partly controlled pre-biologic initiation)

Non-response: No improvement or deterioration

Response: ≥1 category improvement

Post-biologic categories considered for remission definitions (in all patients, irrespective of pre-biologic status)

- Uncontrolled
- Partly controlled
- Well controlled

5.1.4 Lung function

For lung function, post-bronchodilatator FEV1 (absolute value in mL) and FEV1 percent predicted (in %) will be used.

Response definitions (in patients <80% FEV1 predicted pre-biologic initiation)

Non-response: <100mL increase, no change, or decrease

Response: ≥100mL to <200mL increase in FEV1

≥200mL to <500mL increase in FEV1

≥500mL increase in FEV1

As an exploratory analysis, and in an attempt to account for the heterogeneity in patients' geographical location and ethnicity, we will explore different thresholds of relative increase on the FEV1 percent predicted scale.

Post-biologic categories considered for remission definitions (in all patients, irrespective of pre-biologic status)

- <80% FEV1 percent predicted
- ≥80% FEV1 percent predicted

In addition to the definitions provided above, we will explore lung function stability in order to characterize the patients that do not deteriorate over time, which could be considered for both response and remission. Allowing 5% variability on spirometry, the categories will be defined as:

- Deterioration: post-biologic FEV1 <0.95 pre-biologic FEV1
- Stability: post-biologic FEV1 ≥0.95 pre-biologic FEV1

5.2 Composite definitions of response/remission

5.2.1 Response

Eligibility criteria for impairment at biologic initiation and individual domain response definitions described in section 5.1 will be applied for the composite definitions of response. Levels of response will be defined for each composite definition by the number of single domain response criteria met as follows:

1) Exacerbation rates and long-term OCS use

Eligibility criteria: Patients with ≥2 exacerbations in the year preceding biologic initiation & receiving long-term OCS at biologic initiation

Response levels:

- Level 0: meeting none of the response criteria
- Level 1: meeting 1 of the response criteria
- Level 2: meeting both response criteria

2) Exacerbation rates, long-term OCS use, and asthma symptoms control

Eligibility criteria: Patients with ≥2 exacerbations in the year preceding biologic initiation

& receiving long-term OCS at biologic initiation

& being partly or uncontrolled at biologic initiation

Response levels:

Level 0: meeting none of the response criteria

Level 1: meeting 1 of the response criteria

· Level 2: meeting 2 response criteria

Level 3: meeting all 3 response criteria

3) Exacerbation rates, long-term OCS use, asthma symptoms control, and lung function*

Eligibility criteria: Patients with ≥2 exacerbations in the year preceding biologic initiation

& receiving long-term OCS at biologic initiation

& being partly or uncontrolled at biologic initiation

& having FEV1 <80% predicted at biologic initiation

Response levels:

• Level 0: meeting none of the response criteria

Level 1: meeting 1 of the response criteria

• Level 2: meeting 2 response criteria

• Level 3: meeting 3 response criteria

• Level 4: meeting all 4 response criteria

In order to explore composite definitions of response in non long-term OCS users, the variables defined above will be computed in this subgroup of patients after excluding the reduction in long-term OCS daily doses, ie 1) reduction in exacerbations and improvement in asthma symptoms control; and 2) reduction in exacerbations, improvement in asthma symptoms, and improvement in lung function. Other combinations of composite definitions of response (eg, improvement in asthma symptoms control and improvement in lung function alone) will also be explored.

^{*} The response criteria for improvement in lung function will primarily be an increase of at least 100mL in FEV1. Other criteria will be explored.

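### In the three numbered response composites, a patient whose daily OCS dose rose is scored like one with no change and can be placed at an intermediate response level (up to Level 3 of 4), though never at the top

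*Protocol*

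**What the plan says.** Section 5.1.2 of the Protocol splits the OCS domain, among patients on long-term OCS when the biologic starts, into "Non-response: <50% reduction in daily dose from pre- to post-biologic initiation" and "Response: ≥50% reduction in daily dose from pre- to post-biologic initiation". Table 4 in section 5.3 codes the same variable Yes, No or N/A, where the third value is "N/A for patients not receiving long-term" OCS at initiation. Neither place has a class for a dose that went up.

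The other domains are also dichotomised for the composites. Exacerbations: "Response: ≥50% reduction from pre- to post-biologic initiation". Symptom control: "Response: ≥1 category improvement", against "Non-response: No improvement or deterioration". Lung function: at least 100 mL gain in FEV1 as the primary criterion, against "Non-response: <100mL increase, no change, or decrease".

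Section 5.2.1 combines them: "Levels of response will be defined for each composite definition by the number of single domain response criteria met as follows". The three numbered composites use two, three and four domains. All three require long-term OCS use at initiation, so the OCS criterion is scored in every patient they contain. Section 2.2 presents the levels as running from non-response up to the highest response, and section 6.4 uses them as the outcome of ordinal logistic regressions.

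**The concern.** An ordinal outcome is useful if moving up a level means doing better. Here a patient with gains in three domains and a raised OCS dose ties with a patient who has the same gains and a dose cut that fell short of 50%. The same patient ranks above one with two gains and nothing worse.

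OCS is the domain where this matters most, because it is a treatment as well as an outcome. The Background (section 1.0) says that OCS relieves symptoms quickly and that long-term use carries dose-related harm. On the protocol's own account, then, a higher dose is unfavourable in itself and can also improve the other domains that are being counted. If some intermediate-level patients got there with more steroid, the models in section 6.4 would attribute to response to the biologic a pattern that has another possible explanation. Associations with patient characteristics would be blurred accordingly.

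**Working it through.** The protocol gives no figure to reproduce on this point, so the check is of the scoring rules.

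**Step 1: the OCS rule.** Reduction = (pre − post) / pre, with response if this is at least 0.5. The doses below are illustrative only, with 10 mg/day assumed at baseline.

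| Pre → post (mg/day) | Reduction | OCS class |
|---|---|---|
| 10 → 20 | −100% | Non-response |
| 10 → 10 | 0% | Non-response |
| 10 → 6 | 40% | Non-response |
| 10 → 5 | 50% | Response |
| 10 → 0 | 100% | Response |

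An increase, no change and a 40% cut receive the same score.

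**Step 2: the level rule.** With k domains there are 2^k patterns of criteria met or not met, and the level is the number met. With the OCS criterion unmet, the highest possible count is k − 1.

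| Composite (section 5.2.1) | Patterns | Highest level if OCS dose rose | Patterns giving that level | Of these, OCS unmet |
|---|---|---|---|---|
| 1: two domains | 4 | 1 of 2 | 2 | 1 |
| 2: three domains | 8 | 2 of 3 | 3 | 1 |
| 3: four domains | 16 | 3 of 4 | 4 | 1 |

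To reach Level 3 of 4, a patient with a raised dose must meet the exacerbation, symptom and FEV1 criteria.

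**Step 3: the ordering.** In the four-domain composite:
- dose 10 → 20, other three criteria met: Level 3;
- dose 10 → 6, other three criteria met: Level 3;
- dose 10 → 5, two of the other three met: Level 3;
- dose 10 → 10, two of the other three met, none worse: Level 2.

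**Step 4: how many.** Table 5 gives 313, 264 and 134 patients for the three composites. It does not split them by change in OCS dose. Assume that 5-15% have a higher dose at follow-up:
- 313 × 0.05 = 15.7 and 313 × 0.15 = 47.0, so about 16-47;
- 264 × 0.05 = 13.2 and 264 × 0.15 = 39.6, so about 13-40;
- 134 × 0.05 = 6.7 and 134 × 0.15 = 20.1, so about 7-20.

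These are all patients with an increase, at whatever level. If 10-30% of them also met the other three criteria (a second assumption), the number at Level 3 of 4 would run from 6.7 × 0.10 = 0.7 to 20.1 × 0.30 = 6.0, or roughly 1-6 of 134.

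**The case against.** The strongest reply is that the protocol promises a count of response criteria met and delivers one. It nowhere claims a net-benefit scale. A 50% threshold without a worsening class also follows much of what the protocol cites: several responder definitions in Table 2 use such a cut, and in Table 3 a reduction below 50% is the lowest OCS category of the Delphi-based score. This much stands: the rule is a design choice with precedent and does not contradict anything else in the document. It does not remove the ordering problem, because section 6.4 uses the count as an ordinal outcome.

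A second reply is that worsening can be seen elsewhere. Section 6.4 plans cross-tabulations of pre- to post-biologic status, follow-up OCS dose is kept as a number, Table 4 has separate FEV1 decrease categories, and section 5.1.4 adds a deterioration rule. A reader might infer that every domain hides worsening equally. For FEV1 that is not so; OCS change has no comparable category. These items are descriptive, however, and none changes the level that enters a model.

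A third reply concerns the models. If proportional odds fails, section 6.4 compares an extreme level with all others. Top level against the rest is safe, since a patient with a raised dose is never at the top. Level 0 against the rest is not, since such a patient with any gain is grouped with responders.

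The remission composites use the absolute follow-up dose, and the exploratory composites for non-users drop the OCS domain. Neither is affected.

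**Conclusion.** The point holds as a scoring weakness confined to long-term OCS users in the three numbered response composites. A raised dose is scored like no change, and the patient can be placed at Level 1 of 2, 2 of 3 or 3 of 4. It is worth correcting because a higher steroid dose may explain the gains in the other domains.

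Three stronger readings are not supported.
- That steroid-driven improvement is being counted as biologic response: nothing in the documents shows that this occurs, only that the rules would not distinguish it.
- That 16-47, 13-40 or 7-20 patients would be misplaced near the top: those figures rest on an assumed 5-15% and count every patient with an increase. The number at the second-highest level is probably small, about 1-6 of 134 under the further assumption shown.
- That Level 0 commonly mixes stable patients with patients worse in every domain: a patient already uncontrolled at baseline cannot fall a symptom category, so this is possible only for those partly controlled.

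The change is recommended and does not invalidate the planned analysis.

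**What to change.** Keep the planned levels as the main analysis. Then:

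1. From the baseline and follow-up OCS doses already in Table 4, flag patients whose follow-up dose is above baseline, and report their number at each level of each numbered composite.
2. Pre-specify a sensitivity analysis that repeats the section 6.4 models with these patients assigned to Level 0 and, alternatively, excluded. Both versions keep the ordinal outcome well defined.
3. Report worsening in the other domains descriptively, using the protocol's own rule for FEV1 (follow-up below 0.95 of the pre-biologic value). A single category for any worsened domain is best avoided. It would put a patient with three responses and FEV1 just under 0.95 of baseline beside one who is worse throughout, and it would have no rank in an ordinal model.

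The cost is one more row per composite table and a repeat of the model runs, with no new data. Precision will be low in the four-domain group of 134, so the sensitivity result there should be read as a check on direction.
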